#### 10.4.2.4.3 Key Secondary Efficacy Analyses

Each of the following 3 key secondary efficacy endpoints will be analyzed separately using the MMRM model. The terms to be included in the model for each key secondary endpoint are as follows:

- TIS at Week 25: treatment, study visit, the interaction between treatment and study visit, region, and Baseline MMT-8 assessment ( $\leq 142$  points vs.  $> 142$  points), as fixed effects, subjects as a random effect
- Changes from Baseline MMT-8 at Week 25: treatment, study visit, the interaction between treatment and study visit, and region as fixed effects, Baseline MMT-8 as a continuous covariate, subjects as a random effect
- Changes from Baseline CDASI total activity score at Week 25: treatment, study visit, the interaction between treatment and study visit, region, and Baseline MMT-8 assessment ( $\leq 142$  points vs.  $> 142$  points) as fixed effects, Baseline CDASI total activity score as a continuous covariate, subjects as a random effect

Analyses will start with the unstructured covariance matrix; compound symmetry will be adopted in case of convergence difficulties. The differences between treatment sequences, the corresponding 95% CIs, and 1-sided p-values from the models will be provided. Point estimates for the average values in each treatment sequence will be presented along with their standard errors at all visits.

For subjects who receive rescue corticosteroid treatment or who withdraw from treatment or the study, data after the first administration of rescue corticosteroid treatment or withdrawal from randomized IMP treatment will be considered missing and thus not included in the MMRM analysis.

The following sensitivity analyses are planned for the first 3 key secondary endpoints:

- A tipping point analysis as described in [Ouyang, 2017](#) will be performed as a sensitivity analysis. The base case for the tipping point analysis is to include all available data as collected in the MMRM analysis.
- The tipping point analysis will be repeated under the abovementioned hypothetical estimand, ie, where data obtained after rescue corticosteroid treatment or withdrawal from randomized IMP treatment for any reason are excluded from the MMRM analysis.

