1, 3	Individual core set measures (CSMs; except muscle enzyme) and CDASI from Baseline to Week 53	
 
Mean changes from Baseline by treatment sequence between Week 5 and Week 25
 
Mean changes from Week 25 by treatment sequence between Week 29 and Week 53
 
 
Individual CSMs include:
 
 
Physician Global Disease Activity
 
Patient Global Activity Assessment
 
MMT-8
 
Health Assessment Questionnaire – Disability Index
 
Extramuscular Global Assessment
 

Objectives	Endpoints	Summary Measure(s)
1, 3	Definition of Worsening (DOW) from Baseline to Week 53	
 
Number and percentage of subjects meeting DOW at least once, twice, or <math>></math> twice by treatment sequence
 
Time to meeting DOW for the first time by treatment sequence
 
Number and percentage of subjects meeting DOW and receiving rescue corticosteroid treatment by treatment sequence
 

1	Reduction of oral concomitant corticosteroid dose from Baseline to Week 53	
 
Number and percentage of subjects who start oral concomitant corticosteroid dose taper before Week 25 by treatment sequence
 
Number and percentage of subjects who are able to reduce their oral concomitant corticosteroid dose by <math>\geq 25\%</math>, <math>\geq 50\%</math>, and <math>\geq 75\%</math> by Week 25 or by Week 53 by treatment sequence
 

3	Use of rescue corticosteroid treatment from Baseline to Week 25	
 
Percentage of subjects receiving rescue corticosteroid treatment by treatment sequence
 
Percentage of subjects whose rescue corticosteroid treatment is tapered by treatment sequence
 
Time to first administration of rescue corticosteroid treatment
 

Objectives	Endpoints	Summary Measure(s)
1, 3	Mobility, Self-care, and Usual Activities domains of EuroQoL 5-Dimension Questionnaire (EQ-5D-5L) from Baseline to Week 53	
 
Number and percentage of subjects having at least 1 level, 2 levels, and > 2 levels of improvement from Baseline by treatment sequence at Week 13 and Week 25
 
Number and percentage of subjects having no reduction in levels, at least 1 level, 2 levels, and > 2 levels of improvement from Week 25 by treatment sequence at Week 41 and Week 53
 

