## 10.4 Analysis of Key Secondary Endpoints

The following key secondary efficacy endpoints are defined:

- TIS at Week 25
- Changes from Baseline MMT-8 at Week 25
- Changes from Baseline CDASI total activity score at Week 25
- Reduction of oral concomitant corticosteroid dose by at least 25% at Week 25

Each of the following 3 key secondary efficacy endpoints will be analyzed separately using the MMRM. The terms to be included in the model for each key secondary endpoint are as follows:

- TIS at Week 25: treatment, visit, the interaction between treatment and visit, region, and Baseline MMT-8 stratification variable ( $\leq 142$  points vs.  $> 142$  points) as fixed effects, subjects as a random effect;
- Changes from Baseline MMT-8 at Week 25: treatment, visit, the interaction between treatment and visit, and region as fixed effects, Baseline MMT-8 as a continuous covariate, subjects as a random effect;
- Changes from Baseline CDASI total activity score at Week 25: treatment, visit, the interaction between treatment and visit, region, and Baseline MMT-8 stratification variable ( $\leq 142$  points vs.  $> 142$  points) as fixed effects, Baseline CDASI total activity score as a continuous covariate, subjects as a random effect.

Analyses will start with the unstructured covariance matrix; compound symmetry will be adopted in case of convergence difficulties. The differences between treatment sequences, the corresponding 95% CIs, and 1-sided p-values from the models will be provided. Point estimates for the average values in each treatment group will also be presented along with their standard errors.

Only data collected up to the end of Period 1 will be included in the MMRM analysis. For subjects who receive oral rescue corticosteroid treatment or who withdraw from treatment or the study, data after the first administration of oral rescue corticosteroid treatment or withdrawal from randomized IMP treatment will be considered missing and thus not included in the MMRM analysis.

The analysis of the fourth key secondary endpoint, ie, the proportion of subjects who are able to reduce the oral concomitant corticosteroid dose by at least 25% at Week 25 will be done in analogy to the analysis of the primary endpoint, see Section 10.2. The oral concomitant corticosteroid dose at Week 25 will be considered to be reduced by at least 25% when the

---

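### The MMT-8 and CDASI key secondary MMRMs give baseline one common slope over six visits, which may cost precision in the Week 25 tests; a baseline-by-visit term would remove that risk cheaply

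*SAP*

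**What the plan says.** SAP 10.4 lists the terms of each key secondary MMRM. For change in MMT-8 they are "treatment, visit, the interaction between treatment and visit, and region as fixed effects, Baseline MMT-8 as a continuous covariate", plus a subject effect. The CDASI model has "Baseline CDASI total activity score as a continuous covariate", together with treatment, visit, their interaction, region and the MMT-8 stratum. Protocol 10.4.2.4.3 has the same structure; its MMT-8 model ends "and region as fixed effects, Baseline MMT-8 as a continuous covariate, subjects as a random effect". Neither document adds a baseline-by-visit term to these models.

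On covariance: "Analyses will start with the unstructured covariance matrix; compound symmetry will be adopted in case of convergence difficulties". On data: "Only data collected up to the end of Period 1 will be included in the MMRM analysis". SAP Table 1 describes the Period 1 summaries of these measures as "Mean changes from Baseline by treatment sequence between Week 5 and Week 25", and the visit schedule gives six post-baseline visits: Weeks 5, 9, 13, 17, 21 and 25. Only Week 25 is tested (H03 for MMT-8, H04 for CDASI), under the Hommel procedure at an overall one-sided 0.025, once the primary test has succeeded.

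**The concern.** In a model for change from baseline, the regression slope on baseline at a given visit depends on how strongly that visit correlates with baseline. If the correlation decays, the slope becomes more negative with time. There are reasons in the documents to expect some drift. MMT-8 cannot exceed 150 and CDASI activity cannot fall below 0. Subjects may enter on weakness (MMT-8 of 142 or less) or on skin activity (CDASI of 14 or more), so room to improve differs widely between subjects. Improvement is also expected to build over 24 weeks.

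A common slope must compromise across visits. With an unstructured covariance, likelihood weighting favours the early visits, where the residual variance of change is smallest. Week 25, the only visit tested, may then be under-adjusted for baseline. At stake is the width of the Week 25 interval, and so the chance of rejecting H03 and H04.

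**Working it through.** **The plan's only power figure.** SAP Table 3 implies responder rates of 60.25% and 30.9%. Exact one-sided Fisher power at 63 per arm is then 0.904, against 0.905 in SAP Table 14. That figure concerns the primary endpoint. The documents give no SD, correlation or power for MMT-8 or CDASI, so everything below rests on assumed correlations.

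**Set-up (assumed).** Constant SD of 1, complete normal data, six equally spaced visits, no region effect, no scale bounds.

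1. Slope at visit v: b_v = corr(baseline, v) × SD ratio − 1, which here is corr − 1.
2. Common slope: the value b that minimises log|Cov(change − b × baseline)|, the limit of maximum likelihood with unstructured covariance.
3. Week 25 variance inflation: (b_25 − b)² / (1 − corr_25²).
4. Illustrative power, starting from 80% at one-sided 0.025: Φ[(1.960 + 0.842)/√(1 + inflation) − 1.960].

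**Worked case: autoregressive correlation 0.90 per visit, no rating error.** Correlations with baseline run from 0.90 to 0.53, so the slopes run from −0.10 to −0.469. The common slope is −0.143, with 87% of its weight on Week 5 and 10% on Week 25. Residual variance at Week 25 is 1 − 0.53² ≈ 0.718. Inflation is (0.469 − 0.143)²/0.718 = 0.106/0.718 = 14.8%. Power is Φ(2.802/1.071 − 1.960) = 74.4%.

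**Range.** Reliability below 1 multiplies every correlation between different visits, so part of the slope is already present at Week 5.

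| Assumed structure | Slope, Week 5 | Slope, Week 25 | Common slope | Week 25 variance | 80% becomes |
|---|---|---|---|---|---|
| Constant correlation 0.7 | −0.30 | −0.30 | −0.30 | 0% | 80.0% |
| Half stable, half AR 0.95, reliability 0.8 | −0.22 | −0.31 | −0.25 | +0.55% | 79.8% |
| AR 0.95, reliability 0.9 | −0.15 | −0.34 | −0.19 | +3.9% | 78.5% |
| AR 0.90, reliability 0.8 | −0.28 | −0.58 | −0.38 | +4.7% | 78.2% |
| AR 0.90, reliability 0.9 | −0.19 | −0.52 | −0.27 | +8.0% | 76.9% |
| AR 0.85, reliability 0.9 | −0.24 | −0.66 | −0.36 | +10.3% | 76.0% |
| AR 0.90, no rating error | −0.10 | −0.47 | −0.14 | +14.8% | 74.4% |
| AR 0.85, no rating error | −0.15 | −0.62 | −0.24 | +17.5% | 73.4% |

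Random-slope structures gave 0% to 19%, so these rows are scenarios and not bounds.

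**Compound symmetry fallback.** The common slope is then close to the plain average over visits. For AR 0.90 without rating error the average is −0.297, and inflation is (0.469 − 0.297)²/0.718 ≈ 4.1%. Structures with a changing slope gave about 1% to 5.5%, and less where both rating error and slope drift were mild.

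**Simulation check (126 subjects, no rating error, effect set for 90% power with the by-visit slope, 3,000 trials).**

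- Unstratified: variance ratio 1.08 (AR 0.95) and 1.14 (AR 0.90). Power was 0.874 against 0.901, and 0.862 against 0.898. A separate run of 1,500 trials at AR 0.90 gave standard errors of 0.161 and 0.153, a ratio of (0.161/0.153)² = 1.11.
- Randomisation stratified at the baseline median: empirical ratio 1.03 and 1.07, but model-based ratio 1.09 and 1.15. Power was 0.874 against 0.895, and 0.866 against 0.898.
- Type I error: 0.019 to 0.033 with one slope, 0.026 to 0.031 by visit (Monte Carlo standard error about 0.003).
- Constant correlation 0.7: ratio 1.00.

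**The case against.** A pre-specified common-slope MMRM is a legitimate analysis, and nothing in the estimand or hypotheses conflicts with it. Both endpoints are physician-rated and entry uses baseline thresholds. Rating error and regression to the mean should therefore already appear by Week 5, which brings the early slope closer to the late one. The loss is then a few percent in many scenarios and zero if the slope does not drift. The compound symmetry fallback reduces it further. All of this stands, and it is why the loss has to be stated as conditional.

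Stratification at MMT-8 142 also limits chance baseline imbalance for that endpoint. The simulation agrees: the true variance loss roughly halves. The model's standard error stays inflated, however, so the test still loses power. CDASI is not a stratification factor. It is only partly protected, because subjects above 142 must qualify through CDASI and the MMT-8 stratum is in the CDASI model.

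A reader might go further and infer that the Week 25 estimates are biased, or that a fixed share of any baseline imbalance is left in them. The documents do not support this. Randomisation keeps the contrast unbiased with complete data, and the share left (0.33 in the AR 0.90 case) is a worst-case coefficient that acts only on a chance imbalance. Nor can it be said that H03 and H04 lack spare power: no power is stated for them, and the 80% used here is illustrative.

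**Conclusion.** The omission is real and identical in both documents, but its cost is a possible loss of efficiency, not an error of validity. On assumed correlations, Week 25 variance rises by 0% with a constant slope and by about 0.5% to 10% with decaying correlation and rating reliability of 0.8 to 0.9. Without rating error, AR 0.90 to 0.85 gives about 15% to 18%. The matching illustrative power is about 76% to 80%, or 73% to 74% in the upper scenario. A certain loss cannot be claimed, because the documents contain nothing from which the slope's path could be calculated. The scale limits and gradual improvement make some drift plausible and no more.

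The calculations assume complete normal data; dropout, the exclusion of data after rescue, and the scale limits were not modelled. The primary endpoint is unaffected, and so is the TIS MMRM, which has no continuous baseline covariate. The change is worth making because it costs little when the slope is constant and recovers the loss when it is not.

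**What to change.** Before unblinding for the end-of-Period-1 analysis, add Baseline MMT-8 × visit to the MMT-8 MMRM and Baseline CDASI total activity × visit to the CDASI MMRM in SAP 10.4. Because Protocol 10.4.2.4.3 lists the same model terms, either amend it or record the change in SAP Section 5, which at present declares no changes to the protocol's analyses.

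The cost is five degrees of freedom per model (six slopes in place of one) and a declared departure from the protocol model. No new data or visits are needed. The same term in the change-from-reference models of SAP 10.5 is optional and for consistency only, since those p-values are descriptive.

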#### 4.1.1 Inclusion Criteria

To be enrolled and randomized into the study, subjects must meet all of the following inclusion criteria:

- 1 Capable of providing written informed consent by signing an informed consent form (ICF) and willing and able to adhere to all protocol requirements
- 2 Age  $\geq 18$  years
- 3 **Diagnosis** of at least probable IIM per EULAR/ACR Classification Criteria ([Appendix 2](#)): minimum aggregate score of 5.5 without muscle biopsy and 6.7 with muscle biopsy (historical muscle biopsy is acceptable) which includes confirmation of DM rash/skin manifestation (present or by history [historical skin biopsy is required for amyopathic DM subjects])
- 4 **Disease activity** defined by:
  - Presence of DM rash/skin manifestation (eg, Gottron's papules/sign, heliotrope rash, periorbital edema, V sign, Shawl sign) at Screening Visit - OR -

- One objective disease activity measure within 3 months before Baseline:
  - a. Magnetic resonance imaging (MRI) scan showing active inflammation (edema) of a proximal skeletal muscle - OR -
  - b. Electromyogram showing acute changes such as spontaneous activity not explained by other disease - OR -
  - c. Muscle biopsy with perivascular or perimysial inflammation - OR -
  - d. CK > 4 times the upper limit of normal ( $4 \times \text{ULN}$ )

5 **Disease severity** at Screening and Baseline defined by a minimum value of 2 cm on a 10-cm Physician Global Disease Activity VAS\* and:

- MMT-8  $\leq 142$  – OR -
- CDASI total activity score  $\geq 14$

\* On the VAS, 0 cm = absence of disease activity and 10 cm = extremely active/severe disease activity.

6 Subject has failed previous DM treatment or is on DM treatment such as immunosuppressants and/or antimalarials on a stable dose  $\geq 3$  months before Baseline; and/or oral corticosteroids ( $\leq 20$  mg/day prednisolone equivalent) on a stable dose  $\geq 1$  month before Baseline (also see [Section 7.2](#) for details)

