#### **4.4 Randomization Procedures and Blinding**

Eligible subjects will be randomized to 1 of the 2 double-blind treatment sequences by means of Interactive Response Technology (IRT). The IRT will assign the IMP to each subject and the correct dose volume based on the subject's body weight. Randomization will be done centrally and CSL Behring will supply the investigator with a user guide for the IRT.

Randomization will be stratified by region (Japan vs. non-Japan) and by MMT-8 assessment ( $\leq 142$  points vs.  $> 142$  points) to ensure even distribution of subjects to treatment sequences within stratum. For subjects with MMT-8 score at Baseline of  $\leq 142$  points and a muscle group not able to be assessed because of a non-DM related injury or an amputation, the Evaluating Physician will need to determine the appropriate stratification according to DM with muscle weakness (classic DM,  $\leq 142$  points) or DM with little or no muscle weakness (hypo / amyopathic DM,  $> 142$  points) and assign appropriate stratum for this subject.

The randomization list will be generated by the IRT external service provider according to the approved randomization specifications. The IRT external service provider will keep the randomization code on file.

Serum IgG levels will not be disclosed to the investigative site or any blinded study personnel before unblinding the study.

The study data will be unblinded for the primary data analysis (ie, end of Study Period 1 [EOP1] analysis) after all subjects have completed all assessments for Study Period 1 and the data has been cleaned for primary data analysis. CSLB site monitors, subjects and caregivers, as well as site personnel involved in the conduct of the study, will remain blinded to treatment allocation until all subjects have completed all assessments for Study Period 2.

---

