### 8.2.26 Change of Oral Concomitant Corticosteroid Treatment

The change of oral concomitant corticosteroid treatment compares the average daily doses of the treatment in the reference week and the week of interest. The dose at week 1 (ie, the baseline dose) is the dose administered at the baseline date.

$$\begin{aligned} \text{average daily dose week X (mg*)} = \\ \text{sum of all daily doses of week X (mg*) / length week X (days)} \end{aligned}$$

If the length of a week is 0 (see Section 8.2.3) the respective average daily dose will be set to the average daily dose of the subsequent week with length > 0.

#### Change in Week X, for X=2 to 197

$$\begin{aligned} \text{change (\%)} = \\ 100 \times [(\text{average daily dose week X (mg*)} - \text{baseline dose (mg*)}) / \\ \text{baseline dose (mg*)}] \end{aligned}$$

\* mg prednisolone equivalent

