## 9.4 Prior and Concomitant Medications

Prior and concomitant medications will be coded using WHO Drug Dictionary Enhanced (WHO-DDE) 2018 Mar B3 or more recent version, summarized, and listed. The summary of concomitant medications will show the number and percentage of subjects taking prior and concomitant medications. Anatomical Therapeutic Chemical (ATC) classification Level 1 (Body System) information will be included in the data set created but will not appear on the listing or summary.

In the summary of concomitant medications, each subject is counted once within each unique term. For example, if a subject takes Amoxicillin on two separate occasions, the subject is counted only once under the ingredient “Amoxycillin”.

---

Summaries for the following categories will be provided:

- Prior Medication (including corticosteroids) for mITT
- Concomitant Medication (including corticosteroids) for mITT, mITT-EX and for SAF-P3
- Prior Medication (including corticosteroids) to Treat Dermatomyositis for mITT
- Concomitant Medication to Treat Dermatomyositis, excluding Oral Corticosteroids for mITT and mITT-EX
- Oral Rescue Corticosteroid Treatment for mITT
- Oral Concomitant Corticosteroid Treatment, Excluding Oral Rescue Treatment for mITT

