### 10.3 Key Secondary Estimand

The key secondary interest is to quantify the treatment effect of IgPro20 under the hypothetical situation where no subjects receive oral rescue corticosteroid treatment or withdraw from treatment or the study before Week 25.

The key secondary estimands in line with the key secondary interest of the study are described as follows for the continuous key secondary endpoints:

- Population: the target patient population defined by eligibility criteria and who received any amount of randomized IMP treatment and have post baseline efficacy results in Study Period 1 (mITT). For details see Section 6.
- Variables: TIS, changes from Baseline in MMT-8, and changes from Baseline in CDASI total activity score at Week 25
- Intercurrent event: when a subject withdraws from randomized IMP treatment or receives oral rescue corticosteroid treatment before Week 25, data after withdrawal or oral rescue will be considered missing for the continuous endpoints, even if data are collected in the study
- Population-level summary: mean of the variables by treatment sequence

The key secondary estimand for the binary key secondary endpoint reduction of oral concomitant corticosteroid dose by at least 25% at Week 25 is described as follows:

- Population: the target patient population defined by eligibility criteria and who received any amount of randomized IMP treatment and have post baseline efficacy results in Study Period 1 (mITT). For details see Section 6.
- Variables: reduction of oral concomitant corticosteroid dose at Week 25
- Intercurrent events:
  - withdrawal from randomized IMP or the study, which is not related to the Ukraine war, or receiving oral rescue corticosteroid treatment before Week 25: data after withdrawal or oral rescue will be considered no reduction of oral concomitant corticosteroid even if data are collected in the study
  - withdrawal from randomized IMP or the study which is related to the Ukraine war will be addressed using the hypothetical strategy.
- Population-level summary: percentage of subjects who are able to reduce the oral concomitant corticosteroid dose by at least 25% by treatment sequence

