average daily dose of Week 24 is reduced by at least 25%, as treatment with IgPro20 starts in both treatment sequences on the first day of Week 25.

For subjects who do withdraw from IMP or the study for reasons which are related to the Ukraine war before Week 25, the resulting missing values can be considered missing at random (MAR) and multiple imputation will be used to derive the hypothetical post-intervent event reduction of oral concomitant corticosteroid dose in percent (%reduction). Replacement of trailing missing %reduction values for weeks 17 to Week 24 (ie, monotone missings) will be done if the subject received oral corticosteroid medication at baseline using multiple imputations based on monotone regression with the covariates treatment, country, and Baseline MMT-8 ( $\leq$  142 points vs.  $>142$  points), baseline oral corticosteroid dose and %reduction values from previous weeks starting at Week 17 (50 imputations) by SAS® PROC MI. Note: If the subject did not receive any oral corticosteroid medication at baseline %reduction will be set to 0. The multiple imputation process will correspond to the one for the primary endpoint described in Section 10.2. A subject is considered a responder regarding this endpoint, if he/she is able to reduce the oral concomitant corticosteroid dose by at least 25% at Week 24, ie if %reduction is  $\geq 25$ .

For each of the 50 data sets resulting from the multiple imputation process the analysis of the 4th key secondary endpoint will be based on an exact logistic regression model including fixed effects for treatment, region (Japan vs. non-Japan), and Baseline MMT-8 ( $\leq$  142 points vs.  $>142$  points). The corresponding results across the data sets are combined for overall inference using SAS® PROC MIANALYZE according to Rubin's rule.

The 4 key secondary endpoints will be analyzed with an overall 1-sided alpha level of 0.025. The hypotheses associated with the key secondary endpoints will be formally tested and therefore adjusted for multiplicity. The key secondary analyses will be performed based on the mITT and repeated for the PP.

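### Subjects on no oral corticosteroid at baseline count as certain non-responders for the fourth key secondary endpoint (H05), which dilutes its estimate and costs power

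*SAP*

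**What the plan says.** The H05 estimand in SAP 10.3 has the mITT as its population and summarises the "percentage of subjects who are able to reduce the oral concomitant corticosteroid dose by at least 25% by treatment sequence". SAP 10.4 adds: "The key secondary analyses will be performed based on the mITT and repeated for the PP". Protocol 10.4.2.4.1 and 10.4.2.4.3 agree.

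On subjects with no baseline dose, SAP 10.4 and Protocol 10.4.2.4.3 carry the same note: "If the subject did not receive any oral corticosteroid medication at baseline %reduction will be set to 0". A responder needs a reduction of at least 25%, so a value of 0 is always a non-response. The note stands in the paragraph that opens "For subjects who do withdraw from IMP or the study for reasons which are related to the Ukraine war before Week 25".

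Inclusion criterion 6 (Protocol 4.1.1) reads in part: "Subject has failed previous DM treatment or is on DM treatment such as immunosuppressants and/or antimalarials on a stable dose". Oral corticosteroids follow as an and/or option, so a baseline dose of 0 is allowed.

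On design, SAP 4.4 says: "Randomization will be stratified by region (Japan vs. non-Japan) and by MMT-8 assessment". The exact logistic model for H05 has terms for treatment, region and baseline MMT-8 stratum only. The tipping point analyses (SAP 10.4.1) cover only the continuous endpoints, and the key secondary subgroups (SAP 10.4.2) are region and baseline MMT-8. SAP 9.4 lists a descriptive summary: "Oral Concomitant Corticosteroid Treatment, Excluding Oral Rescue Treatment for mITT".

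**The concern.** A subject taking no oral corticosteroid cannot reduce the dose. Keeping such subjects in the denominator makes the reported percentage equal to the user share multiplied by the reduction rate among users. Three things follow.

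- The odds ratio, which is the planned effect measure, moves toward 1, and power falls below that of a users-only test.
- A chance difference between arms in the number of users feeds directly into the comparison, because use is neither stratified nor modelled.
- The result is hard to read, since a low percentage may mean few users or few reductions.

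H05 is one of four hypotheses in the confirmatory Hommel family, so its p-value also affects what can be claimed for the other three.

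The scope of the note is a further gap. If it covers only war-related withdrawals, no rule exists for other non-users. SAP 8.2.26 says: "The change of oral concomitant corticosteroid treatment compares the average daily doses of the treatment in the reference week and the week of interest". Its formula then divides by the baseline dose, which is undefined at 0.

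**Working it through.** **Inputs from the documents.** 63 subjects per arm; one-sided alpha 0.025 for the family, and 0.025/4 = 0.00625 at Hommel Step 4 (SAP 4.2.2). The one-sided Fisher's exact test stands in for the exact logistic model, as in the plan's own power simulation (SAP 4.5).

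**Assumed inputs.** Neither the share f of baseline users nor the reduction rates pA (IgPro20) and pB (placebo) among users is given. I varied f from 0.4 to 0.9 and used (pA, pB) = (0.50, 0.20), (0.45, 0.20), (0.40, 0.15) and (0.60, 0.30).

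**Check of the method on the plan's own figure.** The SAP 4.5 transition probabilities give the primary responder rates.

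- IgPro20: 0.65 × (0.9 × 0.9 + 0.1 × 0.2) + 0.35 × 0.2 × 0.9 = 0.6025
- Placebo: 0.30 × (0.9 × 0.9 + 0.1 × 0.1) + 0.70 × 0.1 × 0.9 = 0.309

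Full enumeration of the Fisher test at 63 per arm gives power 0.904, against 0.905 in SAP Table 14.

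**Direction.** With non-users fixed at zero, the arm rates are f·pA and f·pB. The risk difference is f·(pA − pB) and the risk ratio is unchanged. The odds ratio is [f·pA/(1 − f·pA)] / [f·pB/(1 − f·pB)], which is closer to 1 than the users-only value whenever f < 1. For (0.50, 0.20), where the users-only odds ratio is 4.0:

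- f = 0.6: (0.30/0.70)/(0.12/0.88) = 3.1
- f = 0.9: (0.45/0.55)/(0.18/0.82) = 3.7

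For the test statistic, Z(mITT)/Z(users) is about √[(1 − p̄)/(1 − f·p̄)], where p̄ is the mean of pA and pB. This is below 1 for every f < 1.

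**Power.** All-mITT power uses 63 vs 63 with rates f·pA and f·pB. Users-only power is averaged over binomial(63, f) users in each arm with rates pA and pB.

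| Users | mITT, 50% vs 20% | Users only, 50% vs 20% | Loss over four rate pairs, alpha 0.025 (points) | Loss, alpha 0.00625 (points) |
|---|---|---|---|---|
| 90% | 0.884 | 0.899 | 1.4 to 1.8 | 1.2 to 3.1 |
| 80% | 0.822 | 0.856 | 3.2 to 5.8 | 3.0 to 7.9 |
| 60% | 0.636 | 0.720 | 5.9 to 11.8 | 5.4 to 11.8 |
| 40% | 0.401 | 0.502 | about 7 to 13 | about 5 to 10 |

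Users-only power was higher in all 48 scenarios (six shares, four rate pairs, two alpha levels). A separate set of rate pairs reaching 80% vs 50% gave larger losses: 3 to 14 points at 70% users and 8 to 33 points at 50%.

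**Chance imbalance, 50% vs 20% among users.** Arm rates are (users/63) × 0.50 and (users/63) × 0.20.

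| Users, IgPro20 vs placebo | mITT rates | mITT odds ratio | Users-only odds ratio |
|---|---|---|---|
| 34 vs 42 | 0.270 vs 0.133 | 2.4 | 4.0 |
| 38 vs 38 | 0.302 vs 0.121 | 3.1 | 4.0 |
| 42 vs 34 | 0.333 vs 0.108 | 4.1 | 4.0 |

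At 60% users, a difference of 8 or more users in either direction has probability 0.17; at 90% users it has probability 0.03.

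**Type I error.** With 44 users in each arm and equal true rates of 40% or 60%, the mITT test rejects in 1.0% or 0.6% of trials, so it is conservative. In an extreme split of 50 vs 38 users, the conditional false-positive rate is 9.7% or 17.5%. Randomization averages over such splits, so the unconditional rate is controlled.

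**The case against.** The rule is pre-specified and identical in both documents. The share of all treated patients who cut their steroid dose is a coherent estimand, in the same population as H02 to H04; users-only is a different question. This stands: the rule is a choice and not a contradiction.

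The user share may also be high. Protocol 8.1.2.1 anticipates that subjects come in on corticosteroids already lowered to the permitted maximum or below, and Protocol 1.1 calls corticosteroids the usual first choice. Neither passage gives a percentage, but both point to the upper end of the range, where the loss is under 2 points. This stands as a limit on size.

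Most of the fall in power comes from having fewer informative subjects, which no analysis recovers. With 50% vs 20%, power is 0.931 if everyone is a user and 0.720 for users only at 60% users. Only the further step from 0.720 to 0.636 is due to the analysis. That also stands, and the table counts only that step.

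SAP Table 12 plans percent reduction in average daily dose as a continuous exploratory endpoint, which under SAP 8.2.26 is defined only for users unless the zero rule is carried over. It is descriptive and gives no responder comparison among users. As to the note's scope, covering all non-users is the only workable reading, so that part is a wording fix.

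**Conclusion.** The concern holds. Baseline non-users are certain non-responders in both arms of a confirmatory hypothesis, and nothing in the design or model accounts for them. The odds ratio is diluted and power is lower than it need be whenever the user share is below 1. The direction follows from the text and the algebra. The size depends on the assumed share and rates: under 2 points of power at 90% users and about 6 to 12 points at 60%, for the four main rate pairs at alpha 0.025. Type I error is controlled and no stated power is wrong. This should be changed for efficiency and interpretation; it does not make the test invalid.

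**What to change.** Before unblinding, define the H05 population in Protocol 10.4.2.4.1 and SAP 10.3 as mITT subjects with a baseline oral corticosteroid dose above 0. Use the same population for the secondary summaries of reductions of at least 25%, 50% and 75%. Keep the exact logistic model and the imputation, which is already limited to these subjects. Report the number of users per arm and show the all-mITT result as supportive.

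If the mITT must remain the confirmatory population, add baseline use (yes/no) to the exact model. The non-user stratum has no responders, so conditioning on it gives the same treatment test as users-only. Percentages among users should then be reported too, because the mITT percentages will not match the odds ratio.

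In either case, state the handling of non-users for all subjects, outside the paragraph on war-related withdrawals.

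The cost is wording in both documents, a smaller denominator, a sparser Japan stratum (Protocol 3.5 plans at least 10 Japanese subjects) and, under the first option, a population that differs from H02 to H04. Baseline use is fixed before treatment, so the randomized comparison is kept.
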